12. History of clinically significant cardiac or pulmonary dysfunction, including the following:
 - Grade ≥ 2 hypertension (treated or untreated) or unstable angina
 - Current Grade ≥ 2 dyspnea or hypoxia or need for supplemental oxygen
 - History of symptomatic congestive heart failure of New York Heart Association \geq Class II (see [Appendix 4](#)) or serious cardiac arrhythmia requiring treatment, with the exceptions of atrial fibrillation and paroxysmal supraventricular tachycardia
 - History of myocardial infarction within 6 months prior to first dose of study drug treatment in Cycle 1
 - Current dyspnea at rest due to complications of advanced malignancy or any requirement for supplemental oxygen to perform activities of daily living
 - History of congenital long QT syndrome or QTc > 450 msec.

Central Nervous System:

13. Patients with active CNS lesions are excluded (i.e., those with radiographically unstable, symptomatic lesions). However, patients treated with stereotactic therapy or surgery are eligible if they remain without evidence of disease progression in the brain for ≥ 3 weeks. Whole brain radiotherapy is not allowed with the exception of patients who have had definitive resection or stereotactic therapy of all radiologically detectable parenchymal brain lesions.

General Exclusion Criteria:

14. The patient has not recovered to Grade ≤ 1 from adverse events due to investigational or other agents administered more than 28 days prior to enrollment except for alopecia.
15. Current severe, uncontrolled systemic disease (e.g., clinically significant cardiovascular, pulmonary or metabolic disease)
16. Inability or unwillingness to swallow pills

17. History of malabsorption or other condition that would interfere with enteral absorption of study drug
18. History of clinically significant liver disease (including cirrhosis), current alcohol abuse, or known infection with HIV, hepatitis B virus, or hepatitis C virus
19. Any condition requiring therapeutic anticoagulation (e.g., for chronic atrial fibrillation) with either warfarin, or unfractionated heparin. Note: Patients receiving anticoagulation with low-molecular weight heparin, and low-dose aspirin are eligible, as long as INR and aPTT are $\leq 1.5X$ ULN
20. Use of thrombolytics to establish patency of obstructed indwelling venous catheters is allowed.
21. Prophylactic anticoagulation to maintain patency of venous access devices is allowed as long as INR and aPTT are $\leq 1.5 X$ ULN.

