5.3.4.5 ECG

Triplicate 12-lead ECG should be performed in all patients at following timepoints:

- Screening
- Day -1, Hour 0 (pre-vemurafenib dose)*
Day -1 ECG is not required for previously treated (but without prior exposure to BRAF or MEK inhibitor therapy) or previously untreated for locally advanced/unresectable or metastatic melanoma patients.
- Cycle 1, Day 1, Hour 4 (4 hours post-cobimetinib dose and ± 1 hour)
- Cycle 1, Day 2, Hour 0 (pre-dose)
- Cycle 1, Day 14, Hour 0 (pre-dose) and Hours 2 (± 15 minutes), 4 (± 1 hour) and 8 (± 1 hour) post-dose
- Cycle 1, Day 22, Hour 0 (pre-vemurafenib dose)
- Cycle 2, Day 1
- Cycle 3, Day 1
- Cycle 4, Day 1

*Day -1 ECG is not required for Previously Treated (but without Prior Exposure to BRAF or MEK Inhibitor Therapy) or Previously Untreated for Locally Advanced/Unresectable or Metastatic Melanoma patients.

Following Cycle 4, ECG monitoring should be performed in accordance with the local standard of care, and triplicate ECGs are no longer required. As of Protocol Version K *and future amendments*, central collection of ECGs is no longer required.

Additional ECGs should be performed when clinically indicated. To minimize postural variability, it is important that patients are resting and in a supine position for ≥ 10 minutes prior to each ECG assessment. Blood draws and other procedures should be avoided during the period immediately before ECG measurement, and activity should be controlled as much as possible to minimize variability due to the effects of physical stress. If QTc interval prolongation (>500 msec) is noted on ECG while on study treatment, please refer to the guidelines provided in [Table 12](#) for modification of vemurafenib dosing and subsequent ECG monitoring.

5.3.4.6 Dermatologic Evaluation, Surveillance of Second Primary Malignancies, and Risk Management Plan

Patients will be followed for SCCs (cutaneous and non-cutaneous) and development of any new primary malignancies according to the Risk Management Plan outlined below.

Dermatologic Evaluation

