
I) QTc interval prolongation on ECG
	
On-study QTc interval prolongation to >500 ms but <60 ms increment compared with baseline OR prolongation of QTc interval to ≥60 ms compared with baseline (regardless of absolute QTc):
 
a) Rule out other risk factors for arrhythmia (e.g., myocardial ischemia); check for electrolyte disturbances (particularly potassium and magnesium levels) in all cases.
 
b) Evaluate concomitant medications to determine if there is co-administration of drugs that prolongs QTc interval in all cases (e.g., 5-HT₃ receptor antagonist anti-emetics), see Appendix 6.
 
c) Interrupt dosing of vemurafenib and perform ECG and electrolyte monitoring weekly during period of vemurafenib interruption until QTc improves and electrolytes are corrected in all cases; continue dosing with cobimetinib at the current dose if otherwise tolerated.
 
d) If QTc interval does not improve within 28 days after interruption of vemurafenib dosing, permanently discontinue vemurafenib; continue dosing with cobimetinib at the current dose.
 
e) If QTc improves within 28 days, restart dosing of vemurafenib at one reduced dose level (e.g., 960 to 720 mg bid).
 
f) Repeat 12-lead ECG monitoring at Week 2 and Week 4 of the new, lower vemurafenib dose, at Day 1 of each subsequent Cycle×3, and every 3 months thereafter.
 
g) If second increase in QTc interval to >500 ms occurs at the lower dose of vemurafenib, follow Guidelines a through c above, reduce dose of vemurafenib by 1 more dose level (e.g., 720 to 480 mg bid), and follow Guidelines d and e.
 
On-study QTc interval prolongation to >500ms AND >60 ms increment compared with baseline:
 
a) Patient may continue cobimetinib at his/her current dose level. Vemurafenib treatment may resume if in the investigator’s judgement, the benefit-risk of treatment remains favorable.

J) Hemorrhage
	
Grade 3 events: Interrupt cobimetinib treatment. There are no data on the effectiveness of cobimetinib dose modification for hemorrhage events. Clinical judgment should be applied when considering restarting cobimetinib treatment. Vemurafenib dosing can be continued when cobimetinib treatment is interrupted, if clinically indicated.
 
Grade 4 events or cerebral hemorrhage (all grades): Interrupt cobimetinib treatment. Permanently discontinue cobimetinib for hemorrhage events attributed to cobimetinib.

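### Table 12, QTc row: an ECG with QTc above 500 ms and a rise of more than 60 ms meets both rule blocks, whose vemurafenib restart rules differ, and no precedence is stated

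*Combined protocol and SAP*

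**What the plan says.** Section 5.3.4.5 sends any on-study value above 500 ms to Table 12: "If QTc interval prolongation (>500 msec) is noted on ECG while on study treatment, please refer to the guidelines provided in" that table. Row I then has two blocks.

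**First block.** The trigger has two limbs joined by OR: QTc above 500 ms with a rise under 60 ms, or "prolongation of QTc interval to ≥60 ms compared with baseline (regardless of absolute QTc"). Steps (a)-(c) cover work-up, review of concomitant drugs, and interruption of vemurafenib with weekly ECGs until QTc improves. The later steps are:
- (d) "If QTc interval does not improve within 28 days after interruption of vemurafenib dosing, permanently discontinue vemurafenib".
- (e) "If QTc improves within 28 days, restart dosing of vemurafenib at one reduced dose level".
- (f) "Repeat 12-lead ECG monitoring at Week 2 and Week 4 of the new, lower vemurafenib dose", with later ECGs also scheduled.
- (g) "If second increase in QTc interval to >500 ms occurs at the lower dose of vemurafenib", repeat (a)-(c), go down one more dose level, then follow (d) and (e).

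**Second block.** The trigger is QTc above 500 ms AND a rise of more than 60 ms. The whole instruction is "Patient may continue cobimetinib at his/her current dose level. Vemurafenib treatment may resume" if the investigator judges benefit-risk favourable.

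**The concern.** The two triggers are laid out as alternatives, but the second limb of the first block applies at any absolute QTc, so it already contains the whole of the second block. For those ECGs the table gives two different answers on vemurafenib: a mandatory stop or a one-level reduction under (d)-(e), or a discretionary restart at an unstated dose. Step (g) has the same overlap. Its trigger is a second rise above 500 ms with no condition on the increment, so a second rise that also exceeds 60 ms falls under both (g) and the second block.

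After the same ECG, one site could stop vemurafenib at day 28 or restart it one level lower, while another resumed at the previous dose, each with support in the table. Section 1.2.4.3 describes vemurafenib's QTc effect as concentration-dependent, so whether the dose is reduced matters for the patient.

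**Working it through.** The plan gives no figure to reproduce. The check is logical, followed by a bound on how many patients it could concern.

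**1. Triggers.** Write q for on-study QTc (ms) and d for the rise from baseline (ms).
- First block: (q > 500 and d < 60) or d ≥ 60.
- Second block: q > 500 and d > 60.

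Since d > 60 implies d ≥ 60, the second block lies wholly inside the first. On a 1-ms grid (q from 400 to 600, d from 0 to 150), 100 × 90 = 9,000 points meet both blocks and none meets the second alone.

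| QTc / rise (ms) | First block | Second block |
|---|---|---|
| 510 / 70 | yes | yes |
| 501 / 61 | yes | yes |
| 510 / 60 | yes | no |
| 510 / 50 | yes | no |
| 480 / 70 | yes | no |
| 490 / 30 | no | no |

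**2. Actions when both apply.**

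| | First block | Second block |
|---|---|---|
| No improvement by 28 days | permanent stop (d) | no time limit stated |
| Dose on restart | one level lower (e) | not stated |
| ECGs after restart | schedule (f) | not stated |
| Interruption until QTc improves | step (c) | not stated; arguably carried over, because (c) is worded to cover every case |
| Cobimetinib | continues | continues |

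The clear differences are the 28-day stop and the dose. Schedule (f) is tied to the new, lower dose, so it is unclear whether it follows a restart under the second block. The routine ECGs in Section 5.3.4.5 still apply.

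**3. Is precedence given elsewhere?** Section 5.3.4.5 points to Table 12 without naming a block. Section 6.1.1 says generally that the guidelines do not replace clinical judgement. Section 3.1.5 (DLT definition) and Section 7.1.1.4 (events of special interest) govern counting and reporting. None ranks the two restart rules.

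**4. Size.** Section 1.2.4.3 reports, for 132 patients on vemurafenib 960 mg bid alone, 2 with QTcP above 500 ms and 1 with a change above 60 ms. The joint count is not reported.
- Upper bound: min(2, 1)/132 = 1/132 = 0.76%. Lower bound: 0.
- Applied to about 130 combination patients: 130 × 1/132 = 0.98. Range: 0 to about 1 patient.

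**5. Check of the proposed triggers.** Set the first block to (q > 500 and d ≤ 60) or (d ≥ 60 and q ≤ 500), and leave the second unchanged. On a 1-ms grid (q from 440 to 560, d from 0 to 120), the present wording puts all 3,600 second-block points in the first block too. With the revised triggers, 0 points meet both, 0 lose coverage, 0 are newly covered, and 0 of those now in exactly one block change block.

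**The case against.** The best reply is that the intended reading can be inferred. The first limb's restriction to rises under 60 ms does nothing if the first block also governs larger rises above 500 ms. The second block has its own header for exactly that combination. The same discretionary formula appears in rows B, C, D, E and K as the action for a persistent, recurrent or unexcised event, not as an extra condition on a mandatory stop. A specific-over-general reading is therefore the natural one. This stands as an account of likely intent. But it is nowhere stated, the second limb expressly disregards absolute QTc, and on this reading a rise of 60 ms or more with QTc at or below 500 ms keeps the 28-day stop and dose reduction while the worse combination has neither. If that is intended, the table should say so.

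Safeguards also count. A related Grade 3 or higher event in Cycle 1 is a DLT telephoned within 24 hours, since no listed exclusion covers QTc (Section 3.1.5). Grade 3 or higher QTc prolongation is reported expeditiously (Section 7.1.1.4). The sponsor would therefore hear of such cases, but these sections do not choose the rule.

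Two stronger readings are tempting and should not be drawn.
- *That the overlap is the usual case once QTc exceeds 500 ms.* Exclusion criterion 12 bars "History of congenital long QT syndrome or QTc > 450 msec", so a value of at least 501 ms would mean a rise of at least 501 − 450 = 51 ms if baseline is the screening value. But Table 12 does not define baseline, and a range of possible values is not a frequency. In Section 1.2.4.3, 2 patients exceeded 500 ms and only 1 changed by more than 60 ms, so at least one of the two lay outside the overlap.
- *That the second block has no recovery condition at all.* Step (c) may well bind it, so interruption until QTc improves is arguable.

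**Conclusion.** The point holds as a conflict between stated safety rules. Any ECG with QTc above 500 ms and a rise above 60 ms meets both blocks, their rules on stopping, dose and follow-up ECGs differ, and the protocol does not rank them; step (g) has the same overlap. If the second block is a carve-out, as the layout suggests, the more severe category has the looser rule.

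Severity is minor. The range of 0 to about 1 of 130 patients assumes that the monotherapy rates at 960 mg bid carry over to the combination; five of the ten escalation cohorts use 720 mg bid (Table 5). Fewer patients are probably exposed to the wording at Version L, since a clinical study report has been written (Section 18) and data safety monitoring board review has ceased (Section 10). No estimate, sample size or error rate changes. The overlap itself needs none of these assumptions, because it follows from the trigger wording.

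**What to change.** In one amendment to Table 12, row I:

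1. Make the triggers exclusive. First block: QTc above 500 ms with a rise of 60 ms or less, OR a rise of 60 ms or more with QTc at or below 500 ms. Second block: unchanged.
2. State in the second block that steps (a)-(c) apply, including interruption until QTc improves, and that ECG schedule (f) applies after any restart.
3. Add one sentence to the second block, and one to step (g), saying whether (d)-(e) or investigator discretion governs restart. The clinical choice is the sponsor's. Change 1 should not be made without this one, or the 28-day stop and the dose reduction drop out by default for the most severe category.

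The cost is a wording edit to one table row and a few extra ECGs for a rare patient. Applying schedule (f) to second-block restarts is a small new requirement and should be recognised as such. No new patients or analyses are needed.

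As a clerical aside, footnote 4 of Table 9 sends readers to Table 11, a PK sampling schedule, for ECG monitoring after QTc prolongation. It should point to Table 12.

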6.2 Accountability and Patient Compliance for Investigational Medicinal Product

The investigator is responsible for the control of drugs under investigation. Adequate records for the receipts (e.g., Drug Receipt Record) and disposition (e.g., Drug Dispensing Log) of the study drug must be maintained. Patients will be asked to return all used and unused drug supply containers at the end of the treatment as a measure of compliance.

Accountability and patient compliance will be assessed by maintaining adequate “drug dispensing” and return records.

Accurate records must be kept for each study drug provided by the Sponsor. These records must contain the following information.

- Documentation of drug shipments received from the Sponsor (date received and quantity)
- Disposition of unused study drug not dispensed to patient

A Drug Dispensing Log must be kept current and should contain the following information:

- The identification of the patient to whom the study medication was dispensed
- The date(s) and quantity of the study medication dispensed to the patient.
- The date(s) and quantity of the study medication returned by the patient.

All records and drug supplies must be available for inspection by the study monitor at every monitoring visit.

All study drug required for completion of this study will be provided by Sponsor. The recipient will acknowledge receipt of the drug by returning the appropriate documentation form indicating shipment content and condition. Damaged supplies will be replaced.

Study drug will either be disposed of at the study site according to study site's institutional standard operating procedures or returned to Roche and/Genentech with the appropriate documentation, as determined by the study site. If the study site chooses to destroy the study drug, the method of destruction must be documented.

Roche and/or Genentech must evaluate and approve the study site's drug destruction standard operating procedure prior to the initiation of drug destruction by the study site.

6.3 Formulation, Storage, Packaging, and Labeling

Study drug packaging will be overseen by the Roche clinical trial supplies department and bear a label with the identification required by local law, the protocol number, drug identification, and dosage.

The packaging and labeling of the study medication will be in accordance with Roche standards and local regulations.

The study drug must be stored according to the details on the product label. The drug label indicates the storage temperature.

Local packaging in some countries may be different.

Upon arrival of investigational products at the site, site personnel should check them for damage and verify proper identity, quantity, integrity of seals, and temperature conditions and report any deviations or product complaints to the study monitor upon discovery.

6.3.1 Vemurafenib

Vemurafenib is supplied in 240-mg film-coated tablets packed in bottles for oral administration. For additional batch specific instructions and information for vemurafenib film-coated tablets, see the packaging.

Vemurafenib will be stored at the clinical site under the recommended storage conditions of "Do Not Store above 25°C" as indicated on the study drug label. Patients will be requested to store the vemurafenib at the recommended storage conditions noted on the label, out of the reach of children or other co-inhabitants.

Vemurafenib will be labeled in compliance with Good Manufacturing Procedures. The drug label will include the contents, protocol number, batch number, and storage conditions, as well as any required statements that the drug is "For Investigational Use Only."

6.3.2 Cobimetinib

Cobimetinib will be supplied in two forms: capsules and tablets.

While supplies last, cobimetinib will be supplied as 5-mg, 25-mg, and 100-mg capsules that are differentiated by color. The 5-mg capsules are light blue (Size 1), the

25-mg capsules are orange (Size 1), and the 100-mg capsules are flesh colored (Size 0). The capsule formulation contains no excipients other than the hard gelatin capsule. The capsules should be stored at the clinical site under recommended storage conditions: 15°C–30°C/59°F–86°F, as indicated on the study drug label.

After the capsule supplies are used up or have expired, cobimetinib will be administered in tablet format. The tablet formulation of cobimetinib (GDC-0973) will be a 20-mg film-coated, immediate-release tablet. The tablet formulation consists of the cobimetinib and the following inactive ingredients: microcrystalline cellulose, lactose monohydrate, croscarmellose sodium, magnesium stearate (non-bovine), and Opadry White film coat.

All excipients used in the tablet formulation are compendial (USP/NF and/or EP) grade with the exception of the film coating. The tablet coating consists of polyvinyl alcohol part hydrolyzed, titanium dioxide, polyethylene glycol 3350, and talc. The ingredients in the film coating are compendial. The tablets should not be stored above 25°C (77°F).

The tablet/capsule dose administered to each patient will be based on cohort assignment. Doses will be administered at the clinical site for the initial dose and on subsequent dosing days that coincide with clinical site visits. Patients will be given instructions for self-administration on dosing days that do not coincide with clinical site visits. Any unused study drug must be returned to the study site for disposal. Patients will be asked to store the cobimetinib at the recommended storage conditions noted on the label, out of reach of children or other co-inhabitants.

Cobimetinib packaging will be overseen by the Roche clinical trial supplies department and bear a label with the identification required by local law as well as the protocol number. The packaging and labeling of the study drugs will be in accordance with the Sponsor's standards and local regulations. Local packaging and labeling requirements may differ in some countries.

Upon delivery of the investigational products to the site, site personnel should check for damage and verify proper identity, quantity, integrity of seals, and temperature conditions. Site personnel should report any deviations or product complaints to the study monitor upon discovery.

For further details, see the cobimetinib (GDC-0973) IB.

6.4 Blinding and Un-blinding

This is not applicable as this study is open-labeled.

6.5 Accountability of Investigational Medicinal Product and Assessment of Compliance

6.5.1 Accountability of Investigational Medicinal Product

All records and drug supplies must be available for inspection by the study monitor at every monitoring visit.

Patients will be asked to return all used and unused drug supply containers at the end of the treatment as a measure of compliance. All supplies, including partially used or empty containers and copies of the dispensing and inventory logs, must be returned to the Roche/Genentech monitor at the end of the study, unless alternate destruction has been

authorized by Roche/Genentech or required by local or institutional regulations (Section 6.5.2).

6.5.2 Assessment of Compliance

Patient compliance will be assessed by maintaining adequate study drug dispensing records. The investigator is responsible for ensuring that dosing is administered in compliance with the protocol. Delegation of this task must be clearly documented and approved by the investigator.

Destruction of the Investigational Medicinal Product (IMP)

Local or institutional regulations may require immediate destruction of unused IMP for safety reasons, e.g., cytotoxicity. In these cases, it may be acceptable for investigational site staff to destroy dispensed IMP before a monitoring inspection, provided that source document verification is performed on the remaining inventory and reconciled against the documentation of quantity shipped, dispensed, returned, and destroyed. Written authorization must be obtained from the Sponsor at study start up before destruction.

Written documentation of destruction must contain the following:

- Identity (batch numbers or patient numbers) of investigational product(s) destroyed
- Quantity of investigational product(s) destroyed
- Date of destruction (date discarded in designated hazardous container for destruction)
- Method of destruction (the site must provide the Sponsor with documentation of its institutional policy and procedures for handling and disposing of hazardous drugs)
- Name and signature of responsible person who discarded the investigational product in a hazardous container for destruction

